4.2. General Analytic Approach

[figure not shown]
Medical Oncology and Surgery:

- The primary analysis will include data from both medical oncology (MO) and surgery (Surg) and estimate a common effect of the intervention in MO and SO. An indicator variable (MO vs. Surg), interaction between MO/Surg and Site, and interaction between MO/Surg and background time trend will be included as covariates for adjustment in multilevel generalized linear regression models.
- As a secondary analysis, for each outcome, the heterogeneity of the intervention effect by MO/Surg will also be assessed by the test for interaction between the intervention (eSym yes/no) and MO/surg using multilevel generalized linear regression models. In this analysis, the interaction between the intervention and MO/Surg will be added to the model for the primary analysis.
- As another secondary analysis, we will analyze the data from MO and Surg separately and estimate the intervention effect for each outcome. Note that this analysis is similar to the aforementioned secondary analysis including the interaction between the intervention and MO/Surg. While the aforementioned secondary analysis assumes common effects of patients' characteristics (such as age, race, gender and so on) across MO and Surg, this analysis consider these are possibly different between MO and Surg.

Determination of the intervention and length of follow-up for each episode:

- The presence /absence of the intervention (eSym+ vs. eSym-) is determined in a cross-sectional way at the time of the occurrence of the trigger event
- The follow-up period for each episode is one year from the chemotherapy start date (**MO**) and the date of discharge (**Surg**)

- The intervention determined at the trigger event will never change during the one-year of follow-up period unless another trigger event occurs (see Figure below)

- Some subjects may experience more than one trigger event (i.e., a new chemotherapy treatment plan for **MO** and a qualifying procedure for **Surg**) during the study. Thus, potentially, multiple data points/episodes will be collected from one patient.
- The primary analysis will include all these episodes other than the following episodes:
 - MO episode where its trigger event occurred after the patient was exposed to eSyM Surg, but before eSyM MO was rolled out in the patient's site.

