 - Surg episode where its trigger event occurred after the patient experienced eSyM MO, but before eSyM Surg was rolled out in the patient's site.
 - For example, the 4th episode in the Figure (below) was before go-live of MO in this site and thus this episode is considered eSyM control data(eSyM-). While this patient did not experience the eSyM MO intervention at that time, this patient already experienced the eSyM Surg intervention (eSyM+) (see the 3rd episode in the figure). Therefore, we do not include the 4th episode as eSyM control (eSyM-) data but exclude it from the primary analysis.

[figure not shown]

- As sensitivity analyses, we will perform the analyses using the data consisting of only the first episode from each subject.

Occurrence of another trigger event during the follow-up of an episode:

- If another trigger event (Event B) occurs during the one-year follow-up period of a trigger event (Event A), the data collected after Event B will be included in the aggregation as data of the episode triggered by Event B, not by Event A (Figure below)

Example

Analysis Populations:

All eligible subjects accrued in this study will be included in the primary analysis. To investigate the impact of patient's engagement with eSyM on clinical outcomes, two additional analysis populations will be considered for secondary and exploratory analyses.

To this end, we consider 3 total groups for analysis:

- Group A: episodes where subjects engaged* with eSyM among the eligible episodes of eligible subjects observed in the eSyM intervention (eSyM+) period.
- Group B: episodes where subjects did not engage with eSyM among the eligible episodes of eligible subjects observed in eSyM+.
- Group C: eligible episodes of eligible subjects observed in the eSyM control (eSyM-) period

* Definition of episodes where patient engaged with eSyM: episodes where patient reports ePRO through eSyM at least once during the follow-up

Table 6 shows the details of each analysis population.

Table 6: Analysis Populations and Objectives

Analysis Population	Comparison	Objective	Notes
1) A+B+C	(A+B) vs. C (Primary analysis)	Estimating the effect of eSyM exposure in a future population similar to the entire study population	Exposed to eSyM vs. Unexposed to eSyM regardless of engagement with the exposure (Effectiveness) Clinical outcome data from all groups will be included in the analysis on the basis of the Intention-to-treat principle.

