5.1. Outcomes and summary measures

We do not have preliminary data to support a specific effect size. However, we expect that patients exposed to eSyM may be able to: 1) initiate adjuvant therapy sooner; and/or 2) remain on their chemotherapy regimens for longer duration. These time intervals are straightforward to measure from EHR encounter and date fields. The outcomes for Aim 2b and the projected minimum sample size are summarized in **Table 10**.

Table 10: Outcomes of Aim 2b					
Outcome	Type of outcome	Summary measure for each group	Summary measure for between-group difference	Cohort	Projected minimum sample size
Days from chemo regimen start date to stop date	Continuous	Mean*	Absolute Difference (AD)	All MO	504 patients/site; 3024 MO patients in total 1512 eSyM+ and 1512 eSyM-
Days from surgery date to start of adjuvant chemotherapy	Continuous	Mean*	AD	Surg who get adjuvant Rx (roughly 40% of all Surg)	202 patients/site; 1212 surg patients in total 606 eSyM+ and 606 eSyM-

* Because the maximum follow-up period of each episode is 1 year, the data will be truncated at 365 days when the mean value is calculated.

For MO patients, the outcome is time from the first dose to the last dose of a specific regimen. We will censor follow-up at 1 year. For Surg, the denominator population consists of patients who receive *any* adjuvant chemotherapy within 6 postoperative months. Tumor registry stage distribution at our 6 sites indicates that this will be 202 patients per site or 1212 in total.

The type of censoring involved in this analysis is only the truncation at the maximum follow-up period of 1 year. Thus, we will not employ censored time-to-event analysis methods but handle the outcomes as continuous outcomes.

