This change is necessitated by the observation that the majority of patients did not experience multiple episodes, leading to convergence issues with the generalized linear mixed-effects models initially planned as the primary analysis. Especially in Surgery cohort, only 2.8% subjects had multiple episodes under the intervention condition.

Changes to the Statistical Analysis Plan

1. Multiple episodes for medical record data (page 12)

Original:

- The primary analysis will include all these episodes other than the contaminated episodes.
- As sensitivity analyses, we will perform the analyses using the data consisting of only the first episode from each subject.

Revised:

- The primary analysis will include only the first episode from each subject.
- As sensitivity analyses, we will perform the analyses include all episodes other than the contaminated episodes.

2. Analysis Populations (page 15)

Original:

- 1) The primary analysis population consists of all eligible episodes under the intervention condition (A+B) (i.e., eSyM exposed) and all eligible episodes under the control condition (C) (i.e., eSyM unexposed).

- 2) The secondary analysis population consists of the episodes where patients engaged with eSyM (A) and the matched episodes during the pre-intervention period (C*).

Revised:

- 1) The primary analysis population consists of all 1st eligible episodes under the intervention condition (A+B) (i.e., eSyM exposed) and all 1st eligible episodes under the control condition (C) (i.e., eSyM unexposed).
- 2) The secondary analysis population consists of the 1st episodes where patients engaged with eSyM (A) and the matched 1st episodes during the pre-intervention period (C*).

3. Patient demographic and disease characteristics (Page 16)

Original:

- The unit of the analysis is not patient but episode. All eligible episodes eSyM- episodes will be included in this analysis.

Revised:

- The unit of the analysis is patient in the primary analysis. All eligible 1st episodes will be included in this analysis.

4. Multilevel Generalized Linear Regression Analysis (Page 16)

Original:

- The primary analysis for the outcomes in Aim 2 (Table 5) will be performed via multilevel generalized linear regression models (or generalized linear mixed-effects model; GLMM).
- Subjects
 - o We will potentially have more than one data point from one subject in this study.
 - o To take account of within-subject correlation, subjects will be included as random effects.

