 - o The primary analysis will consider random intercepts only.

Revised:

- The primary analysis for the outcomes in Aim 2 (Table 5) will be performed via generalized linear regression models (or generalized linear model; GLIM).
- Subjects
 - o We will potentially have more than one episode from one subject in this study. However, only the 1st episode from each patient will be included in the primary analysis.
 - o If possible, as a sensitivity analysis, we will perform multilevel generalized linear regression models (or generalized linear mixed-effects model; GLMM) by including all episodes. To take account of within-subject correlation, subjects will be included as random effects.

5. Sensitivity analyses (Page 19):

Original:

- Analysis with data from the first episode
 - o In the primary analysis, all episodes in the analyses except for eSyM- episodes contaminated with the eSyM intervention will be included. We will perform sensitivity analyses using only the first episode from each patient. In these sensitivity analyses, each patient will serve only one data point in the analysis.

Revised:

- Analysis with data from all episodes
 - o In the primary analysis, only the first episode from each patient will be used. In the primary analysis, each patient will serve only one data point in the analysis. We will perform sensitivity analyses using all episodes in the analyses except for eSyM- episodes contaminated with the eSyM intervention will be included.

Implementation and Documentation

These changes will be implemented immediately and documented in all relevant study documents and communications. The SAP addendum will be reviewed and approved by the IRB. All analyses will be conducted based on this SAP addendum.

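### In the all-episode sensitivity analysis, episodes that follow eSyM exposure in the other cohort are dropped from eSyM- but kept in eSyM+, so the arms differ in treatment history by rule

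*SAP*

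**What the plan says.** SAP 4.2 sets the arm of each episode separately: it "is determined in a cross-sectional way at the time of the occurrence of the trigger event". It then defines the all-episode data set: "The primary analysis will include all these episodes other than the following episodes". Two kinds of episode follow. The first is an "MO episode where its trigger event occurred after the patient was exposed to eSyM Surg, but before eSyM MO was rolled out in" that site. The second is a "Surg episode where its trigger event occurred after the patient experienced eSyM MO, but before eSyM Surg was rolled out in" that site. Both are control episodes. The worked example confirms that such an episode is dropped and not recoded: "Therefore, we do not include the 4th episode as eSyM control (eSyM-) data but exclude it from the primary analysis".

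Nothing in 4.2 removes an eSyM+ episode because of what the patient had before.

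The Addendum of June 2024 makes the first episode per patient the primary analysis and moves the all-episode analysis to a sensitivity analysis. Change 1 reads: "As sensitivity analyses, we will perform the analyses include all episodes other than the contaminated episodes". Change 5 asks for sensitivity analyses "using all episodes in the analyses except for eSyM- episodes contaminated with the eSyM intervention", which confirms that only control episodes go. Change 4 runs the mixed model on all episodes only if it proves possible.

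Table 8 adjusts for cohort, site, calendar time, their interactions with cohort, and (Category B) goal of chemotherapy, age, sex, race/ethnicity, rurality and cancer/procedure type. No category contains prior surgery, prior episode or episode order.

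**The concern.** At the Surgery-first sites (LCI, DHMC, WVU), once Surg is live, a patient who goes from surgery to chemotherapy is removed from the MO controls until MO goes live. From that day the same kind of patient counts as eSyM+. The mirror rule does this to patients who go from chemotherapy to surgery at the MO-first sites (BAPT, MMC, DFCI). The case mix therefore changes at the moment the intervention switches on, where site and calendar terms cannot fully absorb it.

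The all-episode analysis was the planned primary and is now the natural check on the change of primary. If its arms differ by rule, agreement or disagreement with the first-episode result could partly reflect the exclusion and not the intervention.

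**Working it through.** **1. The plan's own figures.** Accrual in SAP 3.3: 12 per month x 6 months x 7 periods x 6 sites x 2 cohorts = 6048, as stated. Adjuvant group in SAP Table 10 ("Surg who get adjuvant Rx (roughly 40% of all Surg"): 0.40 x 504 = 201.6, rounded to 202 per site; 202 x 6 = 1212, as stated.

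**2. Inputs.**
- Go-live dates from SAP 3.6, counted from March 2019 to February 2023. For DFCI, the mean of the clinic dates.
- 12 episodes per month per site and cohort (SAP 3.3).
- 56 days from surgery to chemotherapy (SAP 5.3), which is 1.84 months.
- Share f of MO episodes that follow a qualifying in-study surgery: an assumption, 3% to 40%. The 40% in Table 10 is a share of surgical patients. Using it for MO episodes presumes equal cohort sizes, so it is an upper scenario.
- 30-day EDTR risk of 8% in post-surgery MO episodes and 15% in other MO episodes: an assumption. These are the ends of the control range in SAP 4.7, which describes uncertainty about the overall rate and not a contrast between patient types.

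**3. MO control episodes removed.** Removed = (months from Surg to MO go-live - 1.84) x 12 x f. At f = 40%:
- WVU: (29.77 - 1.84) x 4.8 = 134.0
- DHMC: (19.09 - 1.84) x 4.8 = 82.8
- LCI: (9.89 - 1.84) x 4.8 = 38.6

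The total is about 255. MO control months over the six sites are 6.3 + 12.5 + 19.4 + 30.7 + 33.0 + 37.6 = 139.5, or about 1,675 episodes, so 15% are removed. The rule removes nothing at BAPT, MMC and DFCI, where MO went live first.

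**4. Post-surgery share by arm.** Control at f = 40%: (0.40 x 1,675 - 255) / (1,675 - 255) = 415 / 1,420 = 29%, against 40% in eSyM+. At f = 20% it is 13% against 20%; at f = 10%, 6.4% against 10%; at f = 3%, 1.9% against 3%.

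**5. Shift in the estimate with no true effect.** Expected risks on a 5-day grid were fitted by weighted least squares with intervention, site-by-cohort effects and a cohort-specific cubic spline in time. This is Category A without the subject effect, and no Category B adjustment is made.

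| f | Pooled shift (points) | MO-only shift (points) |
|---|---|---|
| 3% | -0.07 | -0.13 |
| 10% | -0.21 | -0.42 |
| 20% | -0.41 | -0.82 |
| 40% | -0.73 | -1.53 |

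With risks of 8% and 12%, the 40% row becomes -0.42 and -0.87. With all episodes kept, the shift is zero in every row, so the rule causes it.

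**6. Mirror rule.** The MO-to-Surg gaps are 31.5 months (BAPT), 19.1 (MMC) and at least 7.4 (DFCI). For assumed risk differences of 3 to 6 points, the MO rule alone shifts the pooled estimate by 0.05 to 0.09 points at f = 5% and by 0.3 to 0.6 at f = 40%. Adding the mirror rule with the same f and an assumed 120-day lag gives 0.09 to 1.3 points if both act in the same direction, and under 0.1 point if they oppose.

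**7. Candidate remedies, at f = 40% and 8% against 15%.**
- SAP exclusion kept, plus a covariate for an earlier event in the other cohort: shift 0.
- Every MO episode after any in-study surgery dropped from both arms: shift 0.
- Only episodes after an eSyM-exposed surgery dropped from both arms: shares become 29% in control and about 22.5% in eSyM+, and about -0.33 (pooled) and -0.73 (MO-only) points remain.

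**The case against.** The exclusion has a sound and stated reason: a control patient who has already used eSyM is a contaminated control. That stands. The gap is the lack of a counterpart on the eSyM+ side, or of a covariate.

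The consequence is limited. A contaminated episode always follows an earlier eSyM+ episode, so it cannot be a patient's first, and the current primary analysis does not contain it. The affected mixed model is a sensitivity analysis that may not be run. This stands and keeps the point minor.

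The size may be very small. The Addendum says most patients had a single episode and gives 2.8% with multiple episodes in the Surgery cohort under intervention. It does not say whether a later MO episode counts, so this figure does not settle f. Goal of chemotherapy, and perhaps age and cancer type, may absorb part of the shift; no adjusted figure can be derived from the documents.

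The counts depend on the date window. The protocol's Activity 4 denominator starts controls on 1/1/2018 and runs eSyM+ to March 31, 2024. On that window the removed share of MO controls falls from 15% to about 10%, but the modelled shift barely changes (-0.75 pooled, -1.57 MO-only at f = 40%).

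A reader might infer that the check is biased towards benefit. The documents do not support that. Nowhere do they say that adjuvant patients have lower EDTR risk, and the mirror rule could add to the shift or cancel it.

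**Conclusion.** The asymmetry is real and follows from the text alone: as written, the all-episode rule makes the arms differ in treatment history, and the difference coincides with go-live. The size and net direction of any resulting bias cannot be determined from the documents. The illustration, for the MO rule only and before Category B adjustment, runs from about -0.07 points pooled (-0.13 MO-only) at a 3% post-surgery share to about -0.7 (-1.5 MO-only) at 40%, against a hypothesised 3 to 4 points. It rests on assumed risks of 8% and 15% and on f, and the 40% end should be read as an upper scenario.

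It would go too far to infer that the trial's primary result is biased, or that the sensitivity analysis must favour eSyM. This is a low-severity point, worth correcting because the correction is cheap and the analysis serves as the check on a change of primary.

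**What to change.** In the all-episode analysis, keep the exclusion of contaminated controls and add one covariate: whether the patient had an earlier in-study trigger event in the other cohort, exposed to eSyM or not. Alternatively, drop every episode preceded by any such event from both arms. In either case, report the episodes removed by site, cohort and arm, which would also show whether the issue matters in practice.

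Do not filter only on an earlier eSyM-exposed episode. Exposure depends on calendar time, so the raw imbalance would reverse and, in the illustration, nearly half of the shift would remain.

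The cost is a sentence in the Addendum and a variable derived from data already held. The downside is one more model term or, with the drop option, fewer episodes in a sensitivity analysis.

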Occurrence of 1 st chemotherapy discontinuation during one-year follow-up period	Time to event	Incidence Rate on (0, 365d)	IRD and IRR	All MO
Occurrence of 1 st admission during one-year follow-up period	Time to event	Incidence Rate on (0, 365d)	IRD and IRR	All MO
Occurrence of 1 st re-operation during one-year follow-up period	Time to event	Incidence Rate on (0, 365d)	IRD and IRR	All Surg
Occurrence of 1 st re-admission during one-year follow-up period	Time to event	Incidence Rate on (0, 365d)	IRD and IRR	All Surg
Death during one-year follow-up period	Time to event	Incidence Rate on (0, 365d)	IRD and IRR	MO and Surg
Composite of EDTR, Hospitalization, and Death event occurrence status at Day 30	Binary	Proportion	Absolute Difference (AD) and Odds Ratio (OR)	MO and Surg
Death during 30-day post-chemotherapy start date (for MO) or at 30-day post-surgical discharge date (for Surg)	Time to event	Incidence Rate on (0, 30d)	IRD and IRR	MO and Surg
Notes:				

 The Day 1 is defined the chemotherapy start date for MO and the discharge date for Surgery. All outcomes are defined in relation to the date of discharge from hospital (for Surg) or the initiation date of a new chemotherapy regimen (for MO). Note that events occurring on the first day of chemotherapy or the day of discharge after surgery will be excluded, because they could not have been impacted by the eSym program. 				

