2) A+C*	A vs. C (Pre-specified Secondary)	Estimating the effect of eSyM exposure in a future population that consists of patients who will engage with eSyM upon exposure.	Exposed to eSyM vs. Unexposed to eSyM conditional on engagement with eSyM (Efficacy) C* is a subset selected from C, so that the case-mix matches A (i.e., Engagement with eSyM). A and B are used to build the propensity score to select C*.
3) A+B	A vs. B (exploratory)	Estimating the effect of eSyM engagement in a future population similar to the study population if everyone engages, under the assumption that everyone in that population engages with eSyM upon exposure.	Engagement with eSyM vs. Unengagement with eSyM, conditioning on everyone being exposed to eSyM Propensity score weighting will be used to adjust for case-mix.
Data collected before go-live (eSyM-)		Data collected after go-live (eSyM+)	
C. Episodes under the control condition		A. Episodes under the intervention condition, where patient engaged with eSyM B. Episodes under the intervention condition, where patient did not engage with eSyM	

- 1) The primary analysis population consists of all eligible episodes under the intervention condition (A+B) (i.e., eSyM exposed) and all eligible episodes under the control condition (C) (i.e., eSyM unexposed).
- 2) The secondary analysis population consists of the episodes where patients engaged with eSyM (A) and the matched episodes during the pre-intervention period (C*). C* is a subset of C. In this analysis, we are interested in estimating the intervention effect among a subgroup of patients who will engage with eSyM if exposed. First, for MO and Surg, a propensity score model (a logistic regression model) to predict engagement with eSyM will be derived using the data from A and B. Next, for each subject in A and C, the predicted probability of engagement will be calculated using the derived propensity score model. The pre-specified variables used for the propensity score models are listed in **Table 7**. For each intervention episode in A, one control episode in C will then be matched, without replacement, based on their predicted probabilities of engagement, using the nearest neighbor matching method stratified by site. The matched dataset is then run through the same outcome model as the primary comparison.

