- 3) As exploratory analyses, we will compare A vs. B. Under the condition that the hospitals have switched on the eSyM system (i.e., everybody is exposed to the eSyM system), we are interested in estimating the effect of the eSyM engagement on the outcomes under the assumption that everyone engages with eSyM, compared to the case where no one engaged with eSyM in spite of eSyM exposure. A propensity score weighting will be used to adjust for the case-mix between engagement with eSyM and non-engagmenet with eSyM. We will build a propensity score model for MO and Surg, separately, using the data from A and B. The pre-specified variables used for the propensity score models are listed in **Table 7**. No outcome model will be involved in this analysis.

Table 7: Pre-specified variables included in the propensity score models

Variable	2) A vs. C*	3) A vs. B	Note
Goal of Chemotherapy (MO with curative goal, MO with palliative goal, Others)	X	X	Only the models for MO
Calendar Time (Secular trends) [continuous with natural cubic spline]		X	
Site (Treating Facility) (DFCI, MMC, DHMC, LCI, BAPT, WVU)	X	X	
Age (year) (fractional polynomials)	X	X	
Sex (male vs. female)	X	X	
Race/Ethnicity (white/non-Hispanic, black/non-Hispanic, Hispanic, Other/Unknown)	X	X	
Employment (Employed, disabled, retired, other)	X	X	
Marital status (married vs. not married)	X	X	
Rurality based on zip code (large metro, small metro, suburban, rural)	X	X	
Insurance type (Medicare only, Medicare and Medicaid, Medicaid only, Private, Other)	X	X	
Cancer type (GI, Gyn, Thoracic)	X	X	
Socio-economic status (quintiles by the zip code-based poverty level)	X	X	
Co-morbidity (Charlson comorbidity index from encounter diagnoses in the 12 months before the first eligibility date) (0, 1, 2+)	X	X	

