4.4. Multilevel Generalized Linear Regression Analysis

The primary analysis for the outcomes in Aim 2 (Table 5) will be performed via multilevel generalized linear regression models (or generalized linear mixed-effects model; GLMM).⁹ The null hypothesis for the statistical test is no intervention effect on the outcome, which indicates that the regression coefficient for the intervention indicator variable is zero. The intervention effect will be summarized in both absolute and relative terms (CONSORT Checklist Item 17b).⁷

Followings are specifications of the GLMM for the primary and secondary analyses.

- Link function
 - For binary outcomes, the logit-link will be used.
 - For count outcomes, the log-link will be used, and the follow-up time will be included as the offset in the model. (Poisson regression)
 - For time-to-event outcomes, we will use Poisson regression models, where the log-link will be used. The event indicator (1: event, 0: censoring) will be the response variable. Exposure time (i.e., days from the start date of the follow-up to either the date of the event occurrence or the end of follow-up, whichever comes first) will be included as the offset in the model.
- Treatment effect metrics
 - Following the recommendation of the CONSORT guideline,⁷ we will report the treatment effect in both absolute and relative metrics.
 - For binary outcomes, we will report odds ratio (OR) derived from the GLMM with the logit-link. In addition, we will calculate absolute difference (AD), using the resulting GLMM with G-computation. Bootstrap will be used to obtain a standard error for the estimated AD.
 - For count outcomes and time-to-event outcomes, we will report the incidence rate ratio (IRR) derived from the GLMM model. In addition, we will calculate absolute difference in incidence rate (i.e., incidence rate difference;IRD) in a similar way to calculate AD.
- Secular trend
 - Primary: Calendar time of the start date of the follow-up of each episode will be included as a continuous variable with natural cubic spline with 3 knots
 - Secondary: Period in which the trigger event occurs will be included as a categorical variable.
- Site (cluster)

- Since there are only 6 sites in this study, the conventional analysis of including cluster as random-effects is problematic due to this small number.¹⁰
- Primary: The primary analysis includes sites as fixed effects.

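### Engagement with eSyM is any report during up to one year of follow-up, with no timing rule, so A vs C* and A vs B carry immortal time for death and can classify episodes after their outcome; the primary comparison is unaffected

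*SAP*

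**What the plan says.** SAP 4.2 (Analysis Populations) splits episodes after go-live into Group A (engaged) and Group B (not engaged), with Group C from before go-live. Engagement is defined as "episodes where patient reports ePRO through eSyM at least once during the follow-up". The same section fixes the length of that follow-up for medical oncology: "The follow-up period for each episode is one year from the chemotherapy start date"; for surgery it is one year from discharge. Follow-up is cut short only by another trigger event or loss.

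Table 6 describes the pre-specified secondary comparison, A vs C*, as "Exposed to eSyM vs. Unexposed to eSyM conditional on engagement with eSyM (Efficacy"). Its stated target is "a future population that consists of patients who will engage with eSyM upon exposure". C* is matched to A on predicted engagement, from a propensity model using the Table 7 variables. Then: "The matched dataset is then run through the same outcome model as the primary comparison". The exploratory A vs B comparison uses propensity weighting only.

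Table 5 sets outcomes at Day 30, Day 90, 180 days and one year. It includes one-year death and "Death during 30-day post-chemotherapy start date (for MO) or at 30-day post-surgical discharge date (for Surg"). For time-to-event outcomes SAP 4.4 counts exposure as "days from the start date of the follow-up to either the date of the event occurrence or the end of follow-up, whichever comes first". SAP 3.4 allows 60 to 180 days of per-protocol use in either cohort, and longer at a site's discretion.

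The June 2024 addendum restricts A and C* to first episodes and leaves the engagement definition as it was.

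**The concern.** Group membership depends on something that happens after follow-up starts. A patient must survive to a first report to enter A. Someone who would have reported but died first is counted in B. C* carries no matching condition, because nobody in C could report. Exposure time in A nevertheless starts at the beginning of follow-up, so the guaranteed-alive days before the first report are credited to A. That is immortal time.

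Separately, a report after Day 30 or Day 90 can place an episode in A once its outcome is already known.

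At stake is an analysis that the plan itself labels as efficacy. Readers may take it as the effect of eSyM in people who use it.

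**Working it through.** **1. Is there a timing rule anywhere?** I looked for a landmark, a time-varying engagement term, or a requirement that the report precede the outcome.

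- Table 7 holds patient, disease, site and calendar-time variables. None reflects when the first report came or survival to it.
- SAP 4.4 treats death as a competing event for ED visits and hospitalization, not as a condition on engagement.
- SAP 4.6 covers recall period, missing data, episode choice and COVID-19.
- The addendum changes the choice of episode and the model.

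None supplies a rule. The plan gives no figure for these comparisons to reproduce, so everything below is illustration under stated assumptions.

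**2. Immortal time for death.** Assumptions not in the documents: no true effect; deaths uniform over the window T; time to first report among would-be engagers exponential with median m; Day-30 mortality d = 2%.

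The chance that the first report precedes a death in the window is s = 1 − (1 − e^(−kT))/(kT), with k = ln 2/m. The death risk seen in A is ds/(ds + 1 − d). For m = 1 and T = 30, kT = 20.8 and s = 1 − 1/20.8 = 0.952; the risk in A is 0.01904/0.99904 = 1.91%.

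| Median first report | s (T = 30) | Death in A | A/C* | A/B* |
|---|---|---|---|---|
| 1 day | 0.952 | 1.91% | 0.953 | 0.910 |
| 2 days | 0.904 | 1.81% | 0.906 | 0.828 |
| 3 days | 0.856 | 1.72% | 0.858 | 0.752 |

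*With an assumed 50% would-be engagers, w = 0.5: risk in B = [wd(1 − s) + (1 − w)d]/[wd(1 − s) + (1 − w)].

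At one year with an assumed 20% mortality, s is 0.996, 0.992 and 0.988, and A/C* is 0.997, 0.994 and 0.991.

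A null simulation of the rate ratio with exposure from the start of follow-up (assumed one-year mortality 10% to 30%, about half ever reporting) agrees. With all first reports on day 2, A vs C is 0.93 to 0.94 at 30 days and 0.99 at one year. If 30% report on day 2 and another 20% spread to day 60, the ratios are 0.65 and 0.96.

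**3. Classification after the outcome.** This is a different mechanism, and the table above does not measure it. At medians of 1, 2 and 3 days the share of first reports after Day 30 is 2^(−30), 2^(−15) and 2^(−10), that is 0.1% or less. If instead a share q of would-be engagers first report after Day 30, that alone gives a risk in A of d(1 − q)/(d(1 − q) + 1 − d). For q = 5%, 10% and 20%, A/C* is 0.95, 0.90 and 0.80.

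**4. ED treat-and-release visits.** If a visit leaves later reporting unchanged, the bias is zero. In the extreme case where every visit stops later reporting (visits uniform over 30 days), replace d by the control risk p, which SAP 4.7 puts at 8% to 15%. For medians of 1, 2 and 3 days, A minus C* is:

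- −0.36, −0.71 and −1.07 points at 8%
- −0.43, −0.87 and −1.32 points at 10%
- −0.62, −1.24 and −1.88 points at 15%

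For the direction, suppose 30 of 50 percentage points of engagement are settled before the event and 20 after. The odds ratio A vs C is then (0.3 + 0.2r)/0.5, where r is the relative chance of later reporting after a visit. It is 0.80 at r = 0.5 (−1.5 to −2.6 points), 1.00 at r = 1, and 1.20 at r = 1.5 (+1.4 to +2.5 points).

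**The case against.** The strongest defence is that first reports are probably early. The sample specification in Protocol Activity 2 starts prompts one day after chemotherapy start or discharge, and on that footing the bias is small. That stands as a limit on size, but no document gives first-report timing.

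The analyses also rank below an intention-to-treat primary comparison. And no outcome list is given for A vs C* or A vs B: the SAP 4.8 shell shows only ED visits and admission. Applying death here is an inference. It is a fair one, because SAP 4.2 introduces these populations for clinical outcomes without restriction and the shell is headed as the primary analysis.

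Follow-up could be read as each outcome's own window. SAP 4.2 defines it as one year; even on the narrow reading, a report could follow the visit and the immortal time would remain.

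Two stronger readings are tempting and not supported:

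- The sample schedule puts about 39 of 48 medical oncology prompts after Day 30 (2 × 24 = 48, less 2 × 30/7 = 8.6). For surgery, 4 to 8 of 14 to 18 prompts fall after week 4. A reader might infer that many patients are classified late. Those counts show opportunity, not when first reports occur.
- For A vs B the SAP says "No outcome model will be involved in this analysis". A reader might count that as a further defect. Weighting without an outcome model is ordinary practice, and a baseline-covariate model would not remove immortal time.

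**Conclusion.** The concern holds for A vs C* and A vs B. The immortal-time component for death favours eSyM. It is modest at Day 30 if first reports come within days (5% to 14% in relative terms), larger if a meaningful share come after Day 30 (5% to 20% for late shares of 5% to 20%), and slight at one year when reports are early (0.3% to 1.0%). All of these rest on assumed mortality, reporting times and no true effect; the actual size cannot be computed from the documents. Net bias also depends on unmeasured differences between engagers and controls.

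A reader might go further and infer that the trial's main result, or the ED-visit result among engagers, is inflated in favour of eSyM. The documents do not support that. In (A+B) vs C, exposure is fixed at the trigger event without regard to engagement. For ED visits the bias is zero unless the visit alters later reporting, and it could then run either way.

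This is worth correcting before the efficacy label is used, but it does not threaten the primary conclusion.

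**What to change.** In order of value:

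1. Report the timing of first eSyM reports relative to deaths and ED visits, by cohort. This shows whether the problem is trivial or material.
2. Describe the any-time A vs C* and A vs B results as associational, not as efficacy, and list the outcomes analysed in each.
3. Add a dated landmark sensitivity analysis beside the existing one, mainly for death. Define engagement as at least one report by a short fixed day, such as Day 7, plus one alternative day. Require A, B and C to be alive at that day, and event-free for binary and first-event outcomes. Refit the propensity score and count outcomes and person-time from the next day. For the 180- and 365-day counts, require survival only and start the count and offset at the landmark.

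In a null simulation (10% ED-visit risk, 2% mortality, visits stopping reports, medians of 1 to 3 days), the any-time rule gave ED-visit rates of 9.6%, 9.1% and 8.7% in A. The Day-7 landmark gave 7.8% to 7.9% in A, B and C, and 1.53% to 1.56% death in A and C.

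The cost is one extra analysis on dates already collected. State its limits:

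- With a constant hazard and gamma frailty variance of 0 to 4, 24% to 32% of Day-30 ED events are lost (for example, at 8% risk without frailty, (1 − 0.92^(7/30))/0.08 = 24%).
- The target narrows to early reporters alive and event-free at the landmark, a status eSyM may itself change. A constant true 3-point benefit shows as 2.0 to 2.4 points. A benefit confined to the first 7 days (hazard halved, −0.8 to −1.6 points over the full window) shows as 0 to +0.8.
- Unmeasured confounding remains.
- The addendum reports convergence problems, so models had been fitted by June 2024 and the addition is post hoc.

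For these reasons it supplements the existing analysis and does not replace it.
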